8.2.2 Analysis

An overview of AEs with onset during TP1 will be provided, showing number and percentage of subjects with at least one:

- AE with onset during TP1
- Treatment-emergent AE on day of first study drug intake
- Treatment-emergent AE on day of re-initiation
- AE with onset during TP1 related to study treatment
- Severe AE with onset during TP1
- AE of special interest with onset during TP1
- SAE with onset during TP1
- SAE related to study treatment with onset during TP1

- Fatal AE with onset during TP1
- AE leading to study drug discontinuation with onset during TP1
- AE leading to study drug interruption with onset during TP1

An overview of AEs with onset during TP2 will be provided, showing number and percentage of subjects with at least one:

- AE with onset during TP2
- AE with onset during TP2 related to study treatment
- Severe AE with onset during TP2
- AE of special interest with onset during TP2
- SAE with onset during TP2
- SAE related to study treatment with onset during TP2
- Fatal AE with onset during TP2
- AE leading to study drug discontinuation with onset during TP2
- AE leading to study drug interruption with onset during TP2

An overview of TEAEs will be provided, showing number and percentage of subjects with at least one:

- Treatment-emergent AE
- Treatment-emergent AE related to study treatment
- Treatment-emergent severe AE
- Treatment-emergent AE of special interest
- Treatment-emergent SAE
- Treatment-emergent SAE related to study treatment
- Treatment-emergent fatal AEs
- AE leading to study drug discontinuation
- AE leading to study drug interruption

AEs will be summarized by presenting the number and percentage of subjects with at least one event, having an AE in each primary SOC, and having each individual AE (PT), for each treatment group.

AEs will be sorted by descending frequency in the highest dose group, then second highest dose group, and so on until the placebo group, and then alphabetically.

Summary tables will be provided for the following:

- AEs with onset during TP1 (by SOC and PT)
- AEs with onset during TP2 (by SOC and PT)
- TEAEs (by SOC and PT)
- TEAEs (by PT)
- TEAEs on day of first study drug intake (by SOC and PT)
- TEAEs on day of re-initiation (by SOC and PT)
- AEs related to study treatment with onset during TP1 (by SOC and PT)
- AEs related to study treatment with onset during TP2 (by SOC and PT)
- TEAEs related to study treatment (by SOC and PT)
- AEs with onset during TP1 (by SOC, PT and intensity)
- AEs with onset during TP2 (by SOC, PT and intensity)
- TEAEs (by SOC, PT and intensity)
- AEs of special interest with onset during TP1 (by SOC and PT)
- AEs of special interest with onset during TP2 (by SOC and PT)
- TEAEs of special interest (by SOC and PT)
- AEs of special interest with onset during TP1 (by category and PT)
- AEs of special interest with onset during TP2 (by category and PT)
- TEAEs of special interest (by category and PT)
- SAEs with onset during TP1 (by SOC and PT)
- SAEs with onset during TP2 (by SOC and PT)
- TESAEs (by SOC and PT)
- Treatment-emergent deaths and SAEs (by SOC and PT)
- Non-serious TEAEs (frequency threshold $\geq 5\%$; by SOC and PT)
- TESAEs (by PT)
- SAEs related to study treatment with onset during TP1 (by SOC and PT)
- SAEs related to study treatment with onset during TP2 (by SOC and PT)
- TESAEs related to study treatment (by SOC and PT)
- Fatal AEs with onset during TP1 (by SOC and PT)
- Fatal AEs with onset during TP2 (by SOC and PT)
- Fatal TEAEs (by SOC and PT)
- AEs leading to temporary interruption of study treatment with onset during TP1 (by SOC and PT)

- AEs leading to temporary interruption of study treatment with onset during TP2 (by SOC and PT)
- AEs leading to temporary interruption of study treatment (by SOC and PT)
- AEs leading to premature discontinuation of study treatment with onset during TP1 (by SOC and PT)
- AEs leading to premature discontinuation of study treatment with onset during TP1 (by PT)
- AEs leading to premature discontinuation of study treatment with onset during TP2 (by SOC and PT)
- AEs leading to premature discontinuation of study treatment with onset during TP2 (by PT)
- AEs leading to premature discontinuation of study treatment (by SOC and PT)

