4.1.5 Safety Analysis Set

The SAF includes all subjects who received at least one dose of double-blind study treatment during TP1. Subjects will be analyzed based on the treatment received. In the event of accidental intake of a treatment other than the randomized treatment, treatment received is defined as the highest dose received.

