Re-initiation in TP1 (during first two weeks of treatment)

- The **‘Date of re-initiation’** is defined as the date when the study treatment was re-initiated after a break of at least 7 days during the first two weeks of treatment in TP1. The date of re-initiation is taken from the Re-initiation / Study Drug Intake eCRF page. Only one re-initiation is permitted per subject during TP1.
- The **‘Time of re-initiation’** is defined as the corresponding time recorded on the Re-initiation / Study Drug Intake eCRF page.

EOS date

- The **‘EOS date’** is taken from the eCRF End-of-Study / Visit Summary form. If this date is missing, the last recorded (follow-up) visit or phone call on the eCRF is considered to be the EOS date.

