8.2 Adverse events

An AE is any event reported by the investigator on the Adverse Event eCRF page.

All AEs will be coded using MedDRA (most current version at time of database closure/snapshot).

AEs are classified according to the period of occurrence of the event. Periods are defined as:

- TEAEs
- AEs with onset during TP1
- AEs with onset during TP2

A more detailed description of rules for assigning AEs to the different periods is described below.

All AE tables will be summarized using the SAF. AE listings (all AEs, AEs leading to premature discontinuation of study treatment, SAEs, AESIs) will be produced using the SAF. A separate listing will be produced using the SCR to present AEs for non-treated subjects.

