8.2.1 Variables

AEs are classified as ‘Treatment-emergent AEs’ if the start date of the AE is on or after the date of first study drug intake (by time and date) up to EOT + 180 days (inclusive).

AEs with onset during TP1 are defined in the interval:

[First study drug intake (by time and date); Month 6 visit or EOT
(if EOT date is on or before Month 6 visit date)]

AEs with onset during TP2 are defined in the interval:

[Month 6 visit + 1 day; EOT].

Any AE prior to start of treatment (by time and date) in TP1 and AEs 121 days or more after EOT are considered non-treatment-emergent AEs.

TEAEs on Day 1 are reported up to 24 hours after first study drug intake in TP1 and on or after the time of first study drug intake.

TEAEs on the day of re-initiation are defined in the same way, but for the day of the re-initiation.

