9 GENERAL STATISTICAL METHODOLOGY

9.1 General rules for data presentations

Unless otherwise specified, data will be summarized using appropriate descriptive statistics:

- For continuous variables: number of non-missing observations, mean, standard deviation, minimum, first quartile, median, third quartile and maximum.

Results will be displayed in the format of the eCRF for median, percentiles, minimum and maximum values. They will be displayed with one additional digit for the mean and the 95% CIs. The standard deviation will be displayed with one more digit than the mean.

- For dichotomous or categorical variables: number of non-missing observations, and frequency with percentage per category. Denominators for percentages are the number of subjects in the pertinent analysis set and treatment group, unless otherwise specified.

- For time-to-event variables: number of events, number at risk, number of censored observations and Kaplan-Meier estimates of the survival function.

In listings, subject number is presented as “SUBJID/SEX/AGE”.

A percentage change from baseline is defined as the absolute change from baseline divided by the baseline value (if the baseline value is > 0) and then multiplied by 100. In the event of baseline and post-baseline value both equal to 0, the ratio to baseline will be set to 1 (i.e., the percent change from baseline will be set to 0%). If baseline is equal to 0 and post-baseline value greater than 0 (infinite ratio) or if baseline greater than 0 and post-baseline equal to 0 ($\log[\text{ratio}] = \text{minus infinity}$), the percent change will be missing.

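### Adverse event percentages for the day of re-initiation are taken over all treated subjects, so they do not show the risk on re-initiation and cannot be compared with the Day 1 row

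*SAP*

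**What the plan says.** Four parts of the SAP together determine the percentage.

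- **Analysis set.** Section 8.2: "All AE tables will be summarized using the SAF". Section 4.1.5: "The SAF includes all subjects who received at least one dose of double-blind study treatment during TP1".
- **Denominator.** Section 9.1: "Denominators for percentages are the number of subjects in the pertinent analysis set and treatment group, unless otherwise specified".
- **Outputs.** Section 8.2.2 lists "Treatment-emergent AE on day of re-initiation" as a row of the TP1 overview, directly under the row for the day of first intake, and "TEAEs on day of re-initiation (by SOC and PT" among the summary tables. The statistic is stated there as well: "AEs will be summarized by presenting the number and percentage of subjects with at least one event, having an AE in each primary SOC". Neither output is given its own denominator.
- **Who can have the event.** Section 8.2.1: "TEAEs on the day of re-initiation are defined in the same way, but for the day of the re-initiation". The model for this is the Day 1 rule, a window of 24 hours from the dose. Section 5.1 defines the re-initiation date as the date on which treatment was "re-initiated after a break of at least 7 days during the first two weeks of treatment in TP1", and allows one re-initiation per subject in TP1.

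The visit schedule in Appendix 12.1 words the break differently. It requires an interruption longer than 7 days between Day 1 and Day 14, whereas section 5.1 also admits a break of exactly 7 days.

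**The concern.** A subject who never re-initiates cannot have an adverse event on a day of re-initiation. Such subjects stay in the denominator as structural zeros. The row above, for the day of first intake, has no such problem, because everyone in the SAF took a first dose. The two rows look alike and invite comparison, but only the upper one estimates a risk per exposed subject.

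The comparison has a clinical purpose. Section 8.6.2.4 states that cenerimod lowers heart rate on the first day of intake, and effects on heart rate and rhythm are a category of special interest in section 8.2.2.1. Appendix 12.1 (notes 7 and 8) repeats the Day 1 hourly ECG and blood pressure monitoring, the discharge check and the 24-hour Holter at re-initiation. A reader will want to know whether restarting carries a first-dose risk.

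Other planned outputs give limited help. Sections 8.6.3.1 and 8.7.1.2.2 name only the day of first intake for their within-day ECG and blood pressure summaries, although section 8.1.1 includes re-initiation in those endpoints. Discharge data from re-initiation are listed, not tabulated (6.8.4.1.2). The two adverse event outputs therefore carry much of the weight.

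**Working it through.** The plan states no re-initiation count or percentage, so there is no figure to reproduce.

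**Inputs**
- Planned sample size of about 325, allocated 1:1:1:1:1 (SAP 2.1): 325 / 5 = 65 per arm. All 65 are assumed to be treated and so in the SAF.
- r, the number re-initiating in an arm: not in the documents. It is an assumption, shown over a range.
- e, the number of re-initiated subjects with an event on that day: illustrative.

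**Formulas**
- Percentage under the SAP: e / 65.
- Proportion among those who could have the event: e / r.
- Ratio of the second to the first: (e / r) / (e / 65) = 65 / r, whatever e is.
- Equivalently, e / 65 = (r / 65) × (e / r). The printed figure mixes how often subjects re-initiate with what happens when they do.

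**Ratio by r**

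| r per arm | r / 65 | 65 / r |
|---|---|---|
| 2 | 3.1% | 32.5 |
| 5 | 7.7% | 13.0 |
| 10 | 15.4% | 6.5 |
| 13 | 20.0% | 5.0 |
| 20 | 30.8% | 3.2 |
| 33 | 50.8% | 2.0 |
| 65 | 100% | 1.0 |

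**Examples**
- 1 event among 3 re-initiators: 1/65 = 1.5% printed, 1/3 = 33.3% among re-initiators.
- 2 among 5: 2/65 = 3.1% and 2/5 = 40.0%.
- 3 among 10: 3/65 = 4.6% and 3/10 = 30.0%.

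**Against the Day 1 row.** Suppose 20% of those dosed have an event on each kind of day, and r = 5. Day 1 shows 13/65 = 20%. Re-initiation shows 1/65 = 1.5%.

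**Between arms.** If the proportion among re-initiators is 20% in two arms, with r = 5 in one and r = 10 in the other, the table shows 1/65 = 1.5% and 2/65 = 3.1%. The difference comes only from the number re-initiating. Whether r does differ between arms is not known from the documents.

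**Search for an exception.** None is written in 8.2, 8.2.1 or 8.2.2, and section 4.1 defines no set of re-initiated subjects. The disposition tables in 6.3 do not include the number re-initiated. Where the SAP departs from the section 9.1 default it says so, as for laboratory (8.4.3), ECG (8.6.3.1) and blood pressure abnormalities (8.7.1.3.2), and reasons for not being of childbearing potential (6.8.1.2).

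**The case against.** The case on the other side has several parts, and much of it limits how strongly the point can be put.

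- **The SAF percentage is not wrong in itself.** It is a valid estimate of the share of treated subjects who had an event on a re-initiation day, and the SAP does not name the risk per re-initiator as a target. This stands. The fault is in what the figure can be read to mean, so calling it a biased estimate would go too far.
- **The size is unknown.** A reader might infer that very few subjects re-initiate and that the dilution is therefore many-fold. The break criterion is narrow, but no count is given, and the ratio falls to 3.2 at 20 re-initiators per arm. Nor does one affected subject out of one to five establish a risk of 20% to 100%: the exact 95% intervals are about 2.5% to 100% for 1/1 and 0.5% to 72% for 1/5.
- **Counts are printed.** An event still appears as a count and is named in the SOC/PT table, so it is not hidden. The discharge listing in 6.8.4.1.2 uses the SAF and would let a reader count re-initiators by arm. The PK summary in 6.10.2 helps less, because its analysis set requires a cenerimod dose and evaluable samples. Recovering r from a listing is possible, but it does not correct the tabulated percentage.
- **Re-initiators are selected after randomization.** Percentages within that subset compare non-randomized groups, whereas the SAF keeps the treated groups together. This stands as a cost of the change.
- **The at-risk rules elsewhere are imperfect precedents.** They mainly exclude subjects already abnormal at baseline or without later values. They show that the SAP writes exceptions when it wants them, and no more than that.

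**Conclusion.** The point holds as a matter of description and interpretation. The denominator follows from sections 8.2, 4.1.5 and 9.1 read together. It yields the share of all treated subjects affected, which is not the risk on re-initiation and is not comparable with the Day 1 row beside it. The gap is a factor of 65/r, assuming 65 treated per arm: for example 13 at r = 5, 6.5 at r = 10 and 3.2 at r = 20.

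The documents do not support three stronger conclusions that a reader might draw: that the dilution is known to be large, that arms are known to differ in how many subjects re-initiate, or that re-initiation would appear free of events. The scope is one overview row and one descriptive safety table. Numerators, efficacy results and hypothesis tests are unaffected.

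**What to change.** - In 8.2.2, state that the re-initiation row of the TP1 overview and the re-initiation SOC/PT table use, as denominator, the number of subjects with a re-initiation date in each treatment group.
- Show that number in the column header beside the SAF N. The SAF percentage can be kept alongside if labelled as the share of all treated subjects.
- State that these percentages are descriptive only, because the subset arises after randomization and may be small.
- Reconcile the break definition in section 5.1 with the one in the Appendix 12.1 schedule, because a subject with a break of exactly 7 days is included by one and not by the other. This defines who is counted.

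The cost is one or two sentences in the SAP, one reconciled definition and one changed denominator in programming; no new data are needed. The price in interpretation is imprecise percentages and a non-randomized comparison between arms, both of which the displayed r makes visible.

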8.2.2.1 AEsIs

AEsIs include important identified or potential risks of the treatment with cenerimod, the known class effects or events that may be related to SLE comorbidities (e.g., cardiovascular AEs).

AEsIs include the following safety categories:

- Effect on HR- and rhythm-related AEs
- Hypotension-related AEs
- Hypertension-related AEs
- Hepatobiliary disorder- / liver enzyme abnormality-related AEs
- Pulmonary-related AEs
- Macular edema- / Eye disorder-related AEs
- Infection-related AEs
- Malignancy (skin)-related AEs
- Malignancy (non-skin)-related AEs
- Cardiovascular-related AEs

AEsIs are identified via PTs provided by the Idorsia Drug Safety department [see Appendix 12.2].

8.3 Death

8.3.1 Variables

Data are taken from the Death eCRF page.

8.3.2 Analysis

Deaths will be summarized using the SAF and listed using the SCR Actual treatment group will be displayed in the listing. Deaths will be summarized by treatment group, SOC and PT.

8.4 Laboratory tests

Laboratory test results are transferred from the central laboratory or, if assayed locally, entered in local laboratory eCRF (in exceptional cases). Local laboratory data will only be listed (as local laboratory data is only requested in specific rare circumstances for medical evaluation of an individual subject).

Laboratory assessments are performed at each scheduled visit from Screening up to the EOS visit (except FU2, FU3, FU3a, and FU3b), and at unscheduled visits if required.

A time window approach will be applied to the laboratory data [as defined in Section 5.4.4].

8.4.1 Measurements

The following parameters are assayed at any scheduled visit according to the protocol:

Hematology:

- Hemoglobin
- Hematocrit, mean corpuscular hemoglobin, mean corpuscular volume, and mean corpuscular hemoglobin concentration
- Erythrocyte count (reticulocyte count)
- Leukocyte count with differential counts (only available after database lock)
- Platelet count

Blood chemistry:

- Aspartate aminotransferase and alanine aminotransferase, alkaline phosphatase, total and direct bilirubin, lactate dehydrogenase
- Creatinine
- Blood urea nitrogen
- Uric acid
- Glucose
- Cholesterol, triglycerides
- Sodium, potassium, chloride, calcium
- Protein, albumin

Urinalysis (including but not limited to):

- pH

- Glucose
- Proteins
- Blood
- Leukocytes

Tests for tuberculosis, viral serology tests (Hepatitis B surface antigen, Hepatitis C antibodies, HIV1 and HIV2 antibodies, varicella-zoster virus IgG antibodies), coagulation tests (prothrombin time, international normalized ratio, activated partial thromboplastin time, urine-protein-to-creatinine ratio), other laboratory tests in the event of infection and pregnancy tests are also carried out during the study.

8.4.2 Variables

The absolute change and percent change from baseline in laboratory parameters (hematology, blood chemistry, and urinalysis) at each post-baseline analysis visit up to EOS is calculated as follows:

- Absolute change in laboratory parameters = Laboratory value at Visit X – Laboratory value at baseline (TP1)
- Percent change in laboratory parameters = (Laboratory value at Visit X – Laboratory value at baseline [TP1]) / Laboratory value at baseline (TP1) × 100

Absolute and percent changes are also derived based on the TP2 baseline.

Laboratory test abnormalities are defined as summarized in protocol appendix 7, for the following periods:

- During TP1: up to Month 6 for subjects who complete TP1 on treatment and up to EOT for subjects who discontinue study treatment during TP1.
- During TP2: up to EOT.
- Treatment-emergent (combining TP1 and TP2 data): up to EOT + 180 days.

